2.2.1 Subgroup of interest

Subgroups will be defined to explore the consistency of treatment effects and safety profiling on selected parameters between the subgroups and the overall population.

In [Table 2-1](#), we have listed all subgroups defined for this study and the ways to derive them. Also note that only important parameters or variables in these analyses will have subgroup analyses. The details about the parameters having subgroup analyses will be presented in the corresponding sections as appropriate. Also, additional subgroups may be formed later for regional or country-wise analyses as applicable.

Table 2-1 Specification of subgroups

Subgroup	Method of derivation	Disposition/ Background & Demographics / Exposure	Efficacy	Safety
Baseline LVEF (< 45% vs. ≥ 45%)	Derived, using data at baseline		x	x

2.3 Patient disposition, demographics and other baseline characteristics

2.3.1 Patient disposition

The number and percentage of patients successfully screened will be presented. In addition, the reasons for screen failures will be provided. For patients who are screened more than once, the information from the last screening will be used in the summary.

The number and percentage of patients completed and failed in the run-in period will be summarized. The reasons for run-in failures will be summarized. The analysis set is the ENR.

The number of patients randomized (RAN), included in the full analysis set (FAS) and safety set (SAF) will be presented by treatment group. The number and percentage of patients who have completed Epoch 3 (treatment period 1) and Epoch 4 (treatment period 2), respectively, will be summarized by treatment group using the RAN. The number and percentage of patients who discontinued and the reasons for discontinuation will be presented for each treatment group using the RAN. The number and percentage of patients with protocol deviations as well as non-protocol deviation criteria leading to exclusion from analysis sets will be presented by treatment group for the RAN.

2.3.2 Demographics and baseline characteristics

The following demographic and baseline characteristics will be summarized by randomized treatment group for patients in the FAS population:

- **Continuous variables**

Age (years)
Height (cm)

Weight at screening (kg)
BMI at screening (kg/m²)
SBP at baseline (mmHg)
DBP at baseline (mmHg)
Pulse at baseline (bpm)
Respiratory rate at baseline (bpm)
eGFR at baseline (mL/min/1.73m²)
LVEF at baseline (%)
NT-proBNP at baseline (pg/mL)
Tobacco consumption (pack year(s))
Alcohol consumption (drink(s) per day)

- **Categorical variables**

Age (<65 years vs. ≥65 years, <75 years vs. ≥75 years)
Sex (Male vs. Female)
Race (Caucasian, Black, Asian, Native American, Pacific Islander, Unknown, Other)
Ethnicity (Hispanic or Latino, East Asian, Southeast Asian, South Asian, West Asian, Russian, Mixed ethnicity, Not reported, Unknown, Other)
Region* (North America, Latin America, Europe, Asia Pacific and Others)
LVEF at baseline (< 45% vs. ≥ 45%)
NYHA class at screening (Class I, II, III, IV)
NYHA class at baseline (Class I, II, III, IV)
NT-proBNP at baseline (< median vs. ≥ median)
Smoker (Never, Current, Former)
Alcohol consumption (0, > 0 - 1, >1 - 2, >2 - 3, >3 drink(s) per day)

* Region is defined as follows:

North America (Canada, United States),
Latin America (Argentina, Guatemala, Mexico),
Europe (Austria, Belgium, Bulgaria, Croatia, Czech Republic, Denmark, Germany, Hungary, Ireland, Italy, Netherlands, Norway, Poland, Spain, United Kingdom),
Asia Pacific and Others (South Korea, Singapore, South Africa, Taiwan)

The above analyses will also be performed by subgroup: baseline LVEF (< 45% vs. ≥ 45%).

2.3.3 Medical history

Any condition entered on the medical history CRF will be coded using the MedDRA dictionary. The number and percentage of patients with each medical history condition will be provided by primary system organ class (SOC), preferred term (PT) and treatment group.

The number and percentage of patients with hypertension and dyslipidemia on the protocol solicited medical history CRF page will be summarized by treatment group. Heart failure and diabetes history will be summarized descriptively by treatment group for the following: prior history of heart failure (yes/no), primary HF etiology (ischemic/no-ischemic), prior heart failure hospitalization (yes/no), number of heart failure hospitalization in the last 12 months and type 2 diabetes history (yes/no). The FAS will be used for the above analyses.

2.4 Treatments (study treatment, rescue medication, concomitant therapies, compliance)

2.4.1 Study treatment / compliance

The duration of double-blind treatment exposure during double-blind period will be summarized by treatment group both descriptively in days (mean, standard deviation, minimum, Q1, median, Q3, and maximum) and by duration category in weeks (≤ 2 , $> 2-4$, $> 4-8$, $> 8-12$, $> 12-24$, > 24) for the SAF.

- Duration of exposure (days) = date of last dose of double-blind study drug – date of first dose of double-blind study drug + 1
- Duration of exposure (weeks) = (date of last dose of double-blind study drug – date of first dose of double-blind study drug + 1)/7

SAF will be used for the above analyses.

2.4.2 Prior, concomitant and post therapies

Prior medications are defined as any recorded medication taken and stopped prior to the date of the first dose of the double-blind study drug.

Concomitant medications for the double-blind period are any medications given at least once between the day of first dose of double-blind study medication and the end of the double-blind period, including those which started pre-BL and continued into the treatment period.

Similarly, prior non-drug therapies are defined as any recorded non-drug therapy taken and stopped prior to the date of the first dose of the double-blind study drug. Concomitant non-drug therapies for the double-blind period are defined as any recorded non-drug therapy given between the day of first dose of double-blind study medication and the end of the double-blind period.

Prior and concomitant medications will be summarized separately by ATC, PT and treatment group. Prior and concomitant non-drug therapies will be summarized separately by primary SOC, PT and treatment group.

The number and percentage of patients meeting rescue criteria and taking rescue medication, and duration of exposure to rescue medication during double-blind period will be summarized by treatment group.

The number and percentage of patients on anti-diabetic medications at baseline (randomization visit) will be summarized by treatment group and medication types as follows:

- Any anti-diabetic medication (insulin or OADs)
 - Insulin
 - OADs (used as single pills)
 - Metformin
 - SU - Sulfonylureas (including Sulfonamides)
 - AGIs
 - TZDs
 - DPP-4 inhibitors
 - GLP-1 analogues
 - Combination of OADs
 - Phenformin + SU
 - Metformin + SU
 - Metformin + TZD
 - SU + TZD
 - Metformin + DPP-4 inhibitor
 - Metformin + AGI
 - DPP-4 inhibitor + TZD
 - Other

The search criteria for the anti-diabetic medications by type are included in [Appendix 5.5](#).

The use of prohibited medications, defined in [Table 2-2](#), will also be summarized.

Table 2-2 Prohibited medication for reporting

Prohibited Medication	Drug record No. or ATC
SGLT2 inhibitors	A10BK
Clarithromycin	00984601
Telithromycin	01548701
Itraconazole	00780701
Ketoconazole	00532501
Voriconazole	01510101
Posaconazole	01762801
Probenecid	00045101
Valproic Acid	00228501
Mefenamic Acid	00044201

The SAF will be used for the above analyses.

2.5 Analysis of primary objective

In general, NT-proBNP data follows a log-normal distribution. Therefore a log-transformation on the NT-proBNP data will be performed before all statistical analyses are carried out. The analysis results will then be back-transformed for ease of data interpretation. The primary endpoint will be analyzed using the FAS.

2.5.1 Primary endpoint

The primary efficacy variable is log-transformed ratio of NT-proBNP (pg/mL) collected at Week 12 to BL (i.e., change from BL in log-transformed NT-proBNP at Week 12).

2.5.2 Statistical hypothesis, model, and method of analysis

The Multiple Comparison Procedure-Modeling (MCP-MOD) method ([Pinheiro et al, 2006](#) & [Pinheiro et al, 2014](#)) as described in the study protocol will not be performed for the primary endpoint. The following analysis will be performed instead as an exploratory analysis for NT-proBNP. Statistical testing of hypotheses on the endpoint will be performed at the two-sided 0.05 significance level.

The change from baseline in log-transformed NT-proBNP at Week 12 will be analyzed using a mixed effect model of repeated measures (MMRM) in which LVEF at baseline (< 45% vs. \geq 45%), treatment group, visit, and treatment group-by-visit interaction will be included as fixed-effect factors, and baseline log-transformed NT-proBNP will be included as a covariate, with a common unstructured covariance matrix for all treatment groups. The analysis will be performed based on change from baseline in log-transformed NT-proBNP at all post-baseline scheduled visits up to Week 12 and based on likelihood method with an assumption of missing at random (MAR) for missing data. Based on the MMRM model, the estimates and the 95% confidence intervals will be provided for the adjusted means of the change from baseline in log-transformed NT-proBNP at Week 4 and at Week 12 for each treatment group, and for the adjusted mean difference at Week 4 and at Week 12.

The treatment effect (mean difference) of LIK066 doses vs. Placebo or LIK066 doses vs. empagliflozin will be analyzed using the MMRM model as described above including all treatment groups: LIK066 2.5mg qd, LIK066 10gm qd, LIK066 50mg qd, Empagliflozin 25mg qd and Placebo qd. For the comparison of LIK066 doses vs. Placebo, the treatment effects of LIK066 2.5mg qd vs. Placebo qd, LIK066 10mg qd vs. Placebo qd, and LIK066 50mg qd vs. Placebo qd will be presented; For the comparison of LIK066 doses vs. EMPA, the treatment effects of LIK066 2.5mg qd vs. Empagliflozin 25mg qd, LIK066 10gm qd vs. Empagliflozin 25mg qd, and LIK066 50mg qd vs. Empagliflozin 25mg qd will be presented. The analysis results will be back-transformed for ease of data interpretation.

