## **5.3 Treatment assignment and randomization**

At Visit 201 (randomization) all eligible patients will be randomized via Interactive Response Technology (IRT) to one of the treatment arms. The investigator or his/her delegate will contact the IRT after confirming that the patient fulfills all the inclusion/exclusion criteria. The IRT

will assign a randomization number to the patient, which will be used to link the patient to a treatment arm and will specify a unique medication number for the first package of study drug to be dispensed to the patient. The randomization number will not be communicated to the user of the IRT system.

The randomization numbers will be generated using the following procedure to ensure that treatment assignment is unbiased and concealed from patients and investigator staff. A patient randomization list will be produced by the IRT provider using a validated system that automates the random assignment of patient numbers to randomization numbers. These randomization numbers are linked to the different treatment arms, which in turn are linked to medication numbers. A separate medication list will be produced by or under the responsibility of Novartis drug supply management using a validated system that automates the random assignment of medication numbers to packs containing the investigational drug(s).

The randomization scheme for patients will be reviewed and approved by a member of the Novartis randomization group.

Randomization will be stratified according to geographical region and LVEF (< 45% versus  $\geq$  45%), see [Section 3.1.3](#).

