**Figure 9-1 Dose-response curve of candidate models**

The analysis to derive the test statistics is based on an analysis of covariance (ANCOVA) model with the log-transformed ratio of NT-proBNP (pg/mL) at Week 12 to baseline as a response variable, treatment (placebo and all LIK066 doses), stratification variables geographical region and LVEF (< 45% versus  $\geq 45\%$ ) as factors, and the baseline in log-transformed NT-proBNP as a covariate. As needed, centers will be pooled according to country and region for the purpose of analysis.

The response variable of log-transformed ratio of NT-proBNP (pg/mL) at Week 12 to baseline used in the above ANCOVA is from an imputed dataset, where the missing Week 12 NT-proBNP is imputed using the multiple imputation method as described in [Section 9.4.3](#). In order to account for the imputation uncertainty, this ANCOVA model will be repeated for each imputed dataset, which results in a set of least squares (LS) mean estimates for all dose groups and the related covariance matrices. Rubin's rule will be used to combine the multiple sets of LS mean estimates and the related covariance matrices to a single set of LS mean estimates of log-transformed ratio of NT-proBNP (pg/mL) at Week 12 to baseline for all dose groups and the related covariance matrix.

The optimal contrasts derived from the candidate model sets will be applied to the combined estimated dose means and covariance matrix to obtain the t statistics for each candidate model and the common critical value  $C_{0.025}$ .  $C_{0.025}$  is the common critical value derived from the reference multivariate t-distribution with the 6x6 correlation matrix induced by testing the candidate dose response models with respect to comparing all LIK doses to placebo group.

The  $H_{01}$  will be rejected and the statistical significance of dose-response in NT-proBNP reduction is established if the  $\max(t_1, t_2, t_3, \dots, t_6) \geq C_{0.025}$ .

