#### **9.4.3 Handling of missing values/censoring/discontinuations**

Missing data for the primary endpoint will be imputed using a multiple imputation approach assuming that the missingness mechanism can be retrieved from observed data (missing at random (MAR)). The imputation model will include the longitudinal sequence of NT-proBNP data collected at baseline, Week 4 and Week 12 visits, stratification factors geographical region and LVEF ( $< 45\%$  versus  $\geq 45\%$ ), and other baseline covariates as appropriate.

The full detailed information about the multiple imputation algorithms will be specified in a separate statistical analysis plan.

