### **Analysis of other continuous outcome variables**

The following continuous variables will be analyzed using the methods described in this section:

- Change from BL in HbA1c at Week 12 and Week 36
- Change from BL in FPG at Week 12 and Week 36
- Change from BL in SBP and DBP at Week 12 and Week 36
- Change from BL in weight at Week 12 and Week 36
- Change from BL in body composition (assessed by bio-impedance) at Week 12 and Week 36
- Percentage change from BL in fasting lipid profile (TG, total cholesterol, HDL cholesterol, LDL cholesterol, calculated VLDL cholesterol and non-HDL cholesterol, lipoproteins (apolipoprotein A-I, apolipoprotein B)) at Week 12 and Week 36
- Change from BL in log-transformed hs-CRP at Week 12 and Week 36
- Change from BL in left atrial size and volume assessed by echocardiography at Week 12 and Week 36

The change from baseline in a continuous outcome at Week 12 (or Week 36) will be analyzed using a mixed effect model of repeated measures (MMRM) in which the stratification variables (geographical region and LVEF < 45% vs.  $\geq$  45%), treatment group, visit, and treatment group-by-visit interaction will be included as fixed-effect factors and baseline outcome variable will be included as a covariate, with a common unstructured covariance matrix for all treatment groups. The analysis will be performed based on change from baseline in the outcome variable at all post-baseline scheduled visits up to Week 12 (or Week 36) and based on likelihood method with an assumption of MAR for missing data. Based on the MMRM model, the estimates and the 95% confidence intervals will be provided for the adjusted means of the change from baseline in the outcome variable at Week 12 (or Week 36) for each treatment group, and for the adjusted mean difference at Week 12 (or Week 36).

For an outcome variable, the treatment effect (mean difference) of LIK066 doses vs. Placebo or LIK066 doses vs. empagliflozin will be analyzed using the MMRM model as described above including all treatment groups: LIK066 2.5mg qd, LIK066 10mg qd, LIK066 50mg qd, Empagliflozin 25mg qd and Placebo qd. For the comparison of LIK066 doses vs. Placebo, the treatment effects of LIK066 2.5mg qd vs. Placebo qd, LIK066 10mg qd vs. Placebo qd and LIK066 50mg qd vs. Placebo qd will be presented; For the comparison of LIK066 doses vs.

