At randomization, patients will be stratified based on geographical region (defined as: North America (Canada, United States), Latin America (Argentina, Guatemala, Mexico), Europe (Austria, Belgium, Bulgaria, Croatia, Czech Republic, Denmark, Germany, Hungary, Ireland, Italy, Netherlands, Norway, Poland, Spain, United Kingdom), Asia Pacific and Others (South Korea, Singapore, South Africa, Taiwan)) and the left ventricular ejection fraction (LVEF) measurement at Visit 101: < 45% versus \geq 45%. Only if the LVEF results from the central reading vendor are not available in time for randomization, the LVEF result from Visit 101 read locally by a cardiologist or from the last measurement (echocardiogram, nuclear study, or left ventricular angiography) done locally prior to enrollment into the study can be used for stratification. The study plans to randomize approximately 496 patients.

Following randomization, patients will attend study visits in Epoch 3 (12 weeks) for the evaluation of the short-term efficacy (change in NT-proBNP), tolerability and safety parameters as defined in Table 6-1 of the study protocol. During Epoch 3, patients will take the study medication as described in Section 5.5.4 of the study protocol.

After completing the procedures required at the last study visit of Epoch 3 (Visit 301), patients will continue in Epoch 4 the treatment they were allocated to in Epoch 3 for another 24 weeks to assess long-term efficacy (by HbA1c, echocardiography and NT-proBNP), tolerability and safety.

The analyses for the abbreviated CSR will be carried out after the completion of the study. There will be no interim analysis.

Figure 1-1 Study Design

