2.1 Data analysis general information

Data will be analyzed by Novartis Biostatistics and Statistical Reporting (SR) according to the statistical analysis Section 9 of the study protocol using SAS Version 9.4 or higher. Data collected during the study will be analyzed after the completion of the study. Due to the early termination of the study, the planned analyses for a full/complete CSR (as outlined in the study protocol) may not provide clinically and/or statistically meaningful results. As a result, only limited planned efficacy analyses (as per study protocol) will be performed (see details in Section 2.5, 2.6.1.2, 2.7.1.2). Treatment group in the following sections refers to LIK066 2.5mg qd, LIK066 10gm qd, LIK066 50mg qd, Empagliflozin 25mg qd and Placebo qd unless specified otherwise.

In general, continuous variables will be summarized descriptively by n, mean, SD, median, minimum (min), Q1 (25th percentile), Q3 (75th percentile) and maximum (max), while categorical variables will be summarized descriptively by count and percentage of patients in each category. Graphical presentation of summary data will also be provided as applicable.

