LIK high dose (n=124) versus placebo (n=124)*	0.5%	1	96%
Any LIK low dose (n=62) versus placebo (n=124)*	0.5%	1	85%

*assuming 10% information loss due to drop-out.

Table 3-3 Comparison of LIK versus empagliflozin

	Expected treatment difference	SD	Probability of the 95% confidence interval upper bound < 0.4%
LIK high dose (n=124) versus EMPA (n=124)	0	1	84%
Any LIK low dose (n=62) versus EMPA (n=124)	0	1	68%

*assuming 10% information loss due to drop-out.

The calculations in Table 3-2 and 3-3 were performed using nQuery 7.0. No multiple testing adjustment was applied.

4 Change to protocol specified analyses

Due to the early termination of the CLIK066B2204 study, the following major changes to the protocol specified analyses have been made in the SAP amendment 1:

- “Week 12 Analysis” and “End of Study Analysis” as defined in the study protocol are no longer applicable. The analyses for the abbreviated CSR will be carried out after the completion of the study.
- MCP-Mod will not be performed for the primary endpoint change in log-transformed NT-proBNP at Week 12. Instead, MMRM will be performed as an exploratory analyses for NT-proBNP. See details in Section 2.5.
- Summary statistics will be provided for selected efficacy endpoints. All efficacy endpoints will be listed. See details in Sections 2.5, 2.6.1.2, 2.7.1.2.
- Subgroup analyses will only be performed for demographics and baseline characteristics, primary and key secondary efficacy endpoints summary statistics, AEs and AEs of special interest, in the subgroups LVEF <45% vs. >= 45%.

5 Appendix

The missing or partially missing AE start/end date and concomitant medication start/end date will be imputed using the Novartis ADaM Governance Board (AGB) global standard approach. Details will be provided in the study Programming Datasets Specifications.

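### The SAP's MMRM for NT-proBNP leaves out geographical region, a randomisation stratification factor that the protocol's models include, without saying so or why

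*SAP*

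**What the plan says.** Both documents make region a stratification factor. Protocol 5.3: "Randomization will be stratified according to geographical region and LVEF". SAP 1.1: "At randomization, patients will be stratified based on geographical region", followed by a definition of four regions by country and by the LVEF split at 45%.

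The protocol carries both factors into every model that its available text specifies:

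- the primary NT-proBNP ANCOVA in 9.4.2, with "treatment (placebo and all LIK066 doses), stratification variables geographical region and LVEF" as factors;
- the imputation model in 9.4.3, with "stratification factors geographical region and LVEF";
- the model for the other continuous endpoints in 9.5.1.2, a "mixed effect model of repeated measures (MMRM) in which the stratification variables (geographical region and LVEF" group) are fixed effects;
- the proportional odds model for NYHA class, also in 9.5.1.2.

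SAP 2.1 says the data will be analysed "according to the statistical analysis Section 9 of the study protocol". It adds that early termination limits the efficacy analyses and refers to Section 2.5. Section 2.5.2 drops MCP-Mod and specifies an MMRM with LVEF group at baseline and then "treatment group, visit, and treatment group-by-visit interaction will be included as fixed-effect factors, and baseline log-transformed NT-proBNP will be included as a covariate". Region is not among the terms.

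SAP Section 4, which lists major changes from the protocol, records the switch from MCP-Mod and continues: "Instead, MMRM will be performed as an exploratory analyses for NT-proBNP. See details in Section 2.5". Neither section mentions region in this connection.

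**The concern.** A factor used to stratify randomisation is normally kept in the analysis model. If it predicts the outcome and the stratification balanced it across arms, the true sampling error of the treatment difference already benefits from that balance. A model that omits the factor leaves its variation in the residual. The reported standard error is then too large, the interval too wide and the test conservative.

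The MMRM is the only model-based test left for the primary endpoint, because SAP 2.6.1.2 reduces the secondary efficacy endpoints to summary statistics and listings. In structure it matches the protocol's own MMRM for continuous endpoints with one term removed. Since nothing is said about the removal, a reader cannot tell a deliberate choice from an oversight.

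**Working it through.** **1. Model terms side by side**

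| Model | Region | LVEF | Baseline value |
|---|---|---|---|
| Protocol 9.4.2, NT-proBNP ANCOVA | yes | yes | yes |
| Protocol 9.4.3, imputation model | yes | yes | yes |
| Protocol 9.5.1.2, MMRM, other continuous endpoints | yes | yes | yes |
| Protocol 9.5.1.2, NYHA model | yes | yes | yes |
| SAP 2.5.2, NT-proBNP MMRM | **no** | yes | yes |

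**2. The plan's own power figure.** Protocol Table 9-1 gives 75% average and 71% minimum power for a 25% reduction at SD 0.85. Optimal contrasts for the six candidate models, with effective group sizes 112/56/56/112 (placebo, 2.5, 10, 50 mg) and a simulated critical value of 2.19, give 74.9% and 71.1%. The figure reproduces. It belongs to the MCP-Mod test that the SAP has abandoned, so the omission of region does not change it.

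**3. Inputs for the MMRM comparison, 50 mg versus placebo**

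- 124 per arm less 10% for missing data: n = 124 × 0.9 = 111.6 (Protocol 9.8).
- SD 0.85 on the log scale (Protocol 9.8), taken here as the SD without region in the model.
- Difference: −ln(0.75) = 0.288, or −ln(0.70) = 0.357.
- Two-sided 0.05 test (SAP 2.5.2).
- R², the share of variance that region explains after baseline NT-proBNP and LVEF: not in the documents. Assumed range 0 to 10%.

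**4. Formulas**

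- SE without region = 0.85 × √(2/111.6) = 0.1138.
- SE with region = 0.1138 × √(1 − R²).
- Power with region = Φ(difference / SE with − 1.96).
- Power without region = Φ((difference − 1.96 × 0.1138) / SE with). The test uses the larger SE, while the estimate varies with the smaller one because regional balance is assumed.

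At R² = 10% and a 25% reduction: with region, Φ(0.288/0.1080 − 1.96) = Φ(0.705) = 76.0%; without, Φ((0.288 − 0.223)/0.1080) = Φ(0.599) = 72.5%.

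| R² | SE with region | SE without / with | Power without → with (25%) | Gain, 25% | Gain, 30% |
|---|---|---|---|---|---|
| 0 | 0.1138 | +0% | 71.5 → 71.5 | 0 | 0 |
| 2% | 0.1126 | +1.0% | 71.7 → 72.4 | 0.7 | 0.4 |
| 5% | 0.1109 | +2.6% | 72.0 → 73.7 | 1.7 | 1.0 |
| 10% | 0.1080 | +5.4% | 72.5 → 76.0 | 3.4 | 1.8 |

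The SE column compares the two models. It is not the excess of the reported SE over true sampling error.

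**5. Simulation check** (4,000 to 5,000 replicates, Monte Carlo error about 0.7 points per power; five arms at 1:1:2:2:2, four regions, two LVEF strata, one visit instead of the full MMRM, and blocks of 8 because the documents give no block size). Gains in points for a 25% reduction:

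| Total N | R² 0 | 2% | 5% | 10% |
|---|---|---|---|---|
| 446 (496 less 10%) | −0.1 | 0.8 | 1.8 | 3.4 |
| 100 (assumed) | −0.1 | 0.5 | 1.2 | 2.9 |
| 60 (assumed) | −0.3 | 0.0 | 0.9 | 1.7 |

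At N = 446, type I error without region was 3.4 to 4.9%, so the test is conservative. With unstratified allocation it was about 5% and the gains were similar (−0.1, 0.8, 2.1, 3.3). At R² = 10% and N = 60 to 200, the reported SE without region exceeded true sampling error by about 3 to 5% with stratified blocks and by about 0 with unstratified allocation.

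**6. Cost in a small sample.** At N = 60 with R² = 0, the SE goes from 0.314 to 0.318 with region (about +1%, stratified blocks), or from 0.323 to 0.332 (about +3%, unstratified allocation). A rough break-even R² is 3/(N − 7): 0.6% at N = 496, 3% at N = 100 and 7% at N = 50. The rule is rough and somewhat pessimistic when stratified blocks balance region, as the two N = 60 results show.

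**7. The other reading of the SD.** If 0.85 is already the region-adjusted SD, and no credit is given for balance, power with region is 71.7% (n = 112) and power without it is 70.8%, 69.4% and 67.1% at R² of 2, 5 and 10%. The largest difference is then 4.6 points, so the table in step 4 is the more cautious version.

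**The case against.** The strongest case against is that this is an exploratory analysis for an abbreviated report of a terminated trial. SAP 2.1 announces limited analyses in the same paragraph that cites protocol Section 9, so that citation does not make the SAP contradict itself. Section 4 claims to list only major changes and points to Section 2.5, where every model term is visible. No passage supports an R² above zero. The power figures at the planned size may describe a trial that did not happen, and with few patients spread over four regions, dropping a multi-level factor and keeping LVEF, the SAP's only listed subgroup, is a defensible simplification.

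Much of this stands as context. The analysis is exploratory, the model is disclosed, R² and the small sample sizes are assumptions, and at about N = 60 the gain can vanish or turn slightly negative. None of it supplies a reason for removing region. The text on limited analyses concerns which analyses are run, not which stratification factors stay in a model that is run. If sparse regions were the reason, the SAP does not say so, and pooling would address it. The SAP still specifies two-sided 0.05 tests and 95% intervals from this model.

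**Conclusion.** The concern holds. Region is a stratification factor, the protocol's models include it, the SAP's NT-proBNP MMRM does not, and Section 4 neither lists nor explains the change. That part rests on the text alone.

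The consequence is modest and conditional. For an assumed R² of 2 to 10%, the SE is 1.0 to 5.4% larger than with region, and the power forgone for 50 mg versus placebo at planned size is 0.7 to 3.4 points (25% reduction) or 0.4 to 1.8 points (30% reduction). It is less at the smaller sample sizes tried and nil if region is not prognostic. To the extent that stratification balanced region, the error is towards conservatism. No bias in the treatment estimate is shown. This change should be made, but the exploratory analysis is not invalid without it.

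**What to change.** In SAP 2.5.2, add geographical region, with the four levels of SAP 1.1, as a fixed-effect factor beside LVEF. Before unblinding, fix a rule for sparse regions. One example is to merge any region with fewer than 16 randomised patients (about two per low-dose arm at 1:1:2:2:2) into the next smallest; the threshold is illustrative. Record the model terms and the pooling rule in SAP Section 4. If the sponsor prefers to leave region out of the main model, Section 4 should say so and why, and a sensitivity MMRM should include it.

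The cost is one model term, one sentence on pooling and one line in Section 4. Region is already collected and defined. The term uses up to 3 degrees of freedom; the downside is an SE about 1 to 3% larger in a sample of about 60 if region has no effect.
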